#### 4.3 Secondary Endpoints

- The percentage of time with platelet response starting from Week 2 until the end of the treatment (EOT) period.
- For each subject, the percentage of time with a platelet response from Week 2 till EOT is calculated as the number of weeks with a platelet response divided by the total number of weeks. Weekly platelet counts are imputed by last observation carry forward using rescue-evaluable weekly platelet counts during the treatment period.
- Descriptive statistics (n, mean, standard deviation, median, Q1 [25th percentile], Q3 [75th percentile], minimum, and maximum) are provided for the average percentage of time across subjects.
- The percentage of time with an increase in platelet count  $\geq 20 \times 10^9/L$  above baseline starting from Week 2 until the end of the treatment period without rescue medication use for ITP in the past 4 weeks.
- For each subject, the percentage of time with an increase in platelet count  $\geq 20 \times 10^9/L$  above baseline from Week 2 till EOT is calculated as the number of weeks with an increase in platelet count  $\geq 20 \times 10^9/L$  above baseline divided by the total number of weeks. Weekly platelet counts are imputed by last observation carry forward using rescue-evaluable weekly platelet counts during the treatment period.
- Descriptive statistics (n, mean, standard deviation, median, Q1 [25th percentile], Q3 [75th percentile], minimum, and maximum) are provided for the average percentage of time across subjects.
- Subject incidence of rescue ITP medications used.
- Total number and percentage of subjects who reported any usage of rescue medications for ITP are calculated with a sub-categorization by preferred terms.
- The incidence of anti-romiplostim neutralizing antibodies and cross reactive antibodies to TPO at any time during the study.
- Number and percentage of subjects who developed anti-romiplostim neutralizing antibodies and/or cross reactive antibodies to TPO by study visits are calculated.
- The incidence of adverse events, including clinically significant changes in laboratory values.
- The summary for adverse events will be performed for the categories of all adverse events, romiplostim-related adverse events, serious adverse events, adverse events leading to withdrawal from the study, adverse events of interest (hemorrhage events, etc.). Both subject incidence and duration-adjusted rates of adverse events are calculated for overall study duration and by study period at every 6 months. Subject listings for all adverse events, serious adverse events, adverse events leading to study withdrawal, and fatal adverse events are provided.

- Summary statistics are calculated for blood chemistry and CBC at each visit. Shift tables between the worst post-baseline and baseline values are provided based on the National Cancer Institute CTCAE, version 3.0.

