6.2.3 Non-responders to Romiplostim

Subjects with a platelet count of < 20 x 10⁹/L for 4 consecutive weeks at the maximum romiplostim dose of 10 µg/kg should be discontinued from romiplostim and will be considered non-responders. Non-responders will be discontinued from the study and undergo all EOT and EOS procedures.

If the subject is a non-responder but the investigator believes the subject has obtained clinical benefit, the investigator must contact the Amgen medical monitor for

Product: Romiplostim
Protocol Number: 20101221
Date: 15 August 2014

Page 28 of 69

consideration of continued participation in the study. If subject is allowed to remain on study and receive a stable romiplostim dose for at least 4 weeks, the subject will be eligible for self- administration.

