7.7 End of Treatment Visit (EOT)

All subjects will complete an EOT visit. For subjects who complete the 36-month treatment period and who have been off romiplostim and other medications for ITP (concomitant or rescue) for 4 weeks or more, the EOT visit will be the final study visit and will occur after the completion of the 36-month treatment period. For subjects ending the 36-month treatment period for non-response or other reasons while still receiving romiplostim, this visit will be 1 week after the last administration of romiplostim.

The following assessments will be completed at the EOT visit:

- physical exam, including vital signs
- documentation of concomitant and rescue medications
- adverse event reporting
- central lab CBC with differential and blood chemistry
- local lab platelet counts
- collection of blood samples for anti-romiplostim antibodies
- local lab peripheral blood smear
- local lab urine or serum pregnancy test for female subjects of child-bearing potential (defined as having first menses)

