### 2.2 Secondary

The secondary objectives of the study are:

- To describe the percentage of time that pediatric subjects with ITP have a platelet response over the study duration
- To describe the percentage of time that pediatric subjects with ITP have an increase in platelet count  $\geq 20 \times 10^9/L$  above baseline over the study duration
- To describe the use of rescue ITP medications
- To describe the incidence of antibody formation
- To describe the safety of romiplostim as a long-term treatment in pediatric thrombocytopenic subjects with ITP

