## **4. Study Endpoints and Covariates**

### **4.1 Study Endpoints**

#### **4.2 Primary Endpoint**

The primary endpoint is the percentage of time with a platelet response, defined as a platelet count of  $\geq 50 \times 10^9/L$  without rescue medication use for ITP in the past 4 weeks, starting from Week 2 in the first 6 months of the treatment period.

A rescue-evaluable weekly platelet count is defined as a weekly platelet count without rescue medication use for ITP in the past 4 weeks.

In the first 6 months of treatment period, a monthly platelet response is defined as a the median of rescue-evaluable platelet counts of  $\geq 50 \times 10^9/L$ .

For each subject, the percentage of time with platelet response during the first 6 months is calculated as the number of monthly platelet response divided by the total number of months. If the monthly platelet response is missing, it will be imputed based on the neighboring monthly platelet response status and rescue medication use in the month. If a monthly platelet response is still missing after imputation, it is considered as no response in this month. Subjects who discontinued the treatment early due to lack of

response (non-responder to romiplostim) before completing 6 months of treatment, the month(s) following their discontinuation of treatment till the 6th month will be imputed as having no monthly platelet response.

The primary endpoint is summarized by descriptive statistics (n, mean, standard deviation, median, Q1 [25th percentile], Q3 [75th percentile], minimum, and maximum) of this percentage of time with platelet response averaging across subjects.

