#### 6. Definitions

| Term                                      | Definition/Explanation   |
|---|--|
| End of study for individual subject (EOS) | Defined as the last day that protocol-specified procedures are conducted for an individual subject   |
| End of treatment (EOT)                    | Defined as the last assessment for the protocol-specified treatment phase of the study for an individual subject   |
| End of study (primary completion)         | Defined as the time when the last subject is assessed or receives an intervention for the purposes of final collection of data for the primary outcome. This will occur once the last subject participating has completed the EOS visit. |
| Interactive Voice Response System (IVRS)  | Telecommunication technology that is linked to a central computer in real time as an interface to collect and process information.   |

| Term                                      | Definition/Explanation   |
|---|--|
| Study Day 1                               | Defined as the first day that romiplostim is administered to the subject   |
| Study Week 1                              | Defined as the week that the first dose of romiplostim is administered to the subject                                    |
| Study day                                 | Defined as (calendar date – first dose date) +1  |
| Study treatment period                    | Defined as the period from the date of first dose of romiplostim till the date of last dose of romiplostim plus one week |
| Treatment duration for individual subject | Defined as the (last dose date – first dose date)+7 days   |
| Baseline Platelet Count                   | The average of available platelet counts obtained at screening and pre-treatment prior to dosing.                        |
| Study baseline                            | Other than for platelet count, the baseline is defined as data immediately prior to first dose administration            |
| Platelet response                         | Defined as platelet count of $\geq 50 \times 10^9/L$ without rescue medication use for ITP in the past 4 weeks           |

Page 2 of 2

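### SAP 4.3 ends both long-term percentage-of-time endpoints at EOT, so for children who respond, lose response and are stopped they overstate time in response over the study duration and follow a different rule from SAP 4.2

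*SAP*

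**What the plan says.** The SAP treats one event, a stop for lack of response, in two ways.

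- **Primary endpoint (SAP 4.2).** For children who stop as non-responders before completing 6 months, "the month(s) following their discontinuation of treatment till the" sixth are imputed as no monthly response. The denominator stays at six months.
- **Long-term endpoints (SAP 4.3).** The percentage of time in response from Week 2 till EOT "is calculated as the number of weeks with a platelet response divided by the total number of weeks". Weekly counts are "imputed by last observation carry forward using rescue-evaluable weekly platelet counts during the treatment period". The endpoint based on a rise of at least 20 x 10⁹/L above baseline is built the same way. Neither has a rule for weeks after a lack-of-response stop, and the total number of weeks is not defined further.
- **End of the clock.** For a child who ends treatment for non-response while on drug, Protocol 7.7 says of EOT that "this visit will be 1 week after the last administration of romiplostim". The entry for study treatment period in SAP 6 reads "Defined as the period from the date of first dose of romiplostim till the date of last dose of romiplostim plus one week". Protocol 6.2.3 adds: "Non-responders will be discontinued from the study and undergo all EOT and EOS procedures".
- **Objective (SAP 2.2).** "To describe the percentage of time that pediatric subjects with ITP have a platelet response over the study duration". Protocol 10.1.1, by contrast, words the endpoint as running only to the end of the treatment period.

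SAP 11 declares no changes from the protocol and does not comment on the difference.

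**The concern.** For a child who responds, loses response and is stopped for that reason, the clock stops because of the outcome being measured. The child keeps the percentage earned before failing, and the rest of the planned 36 months drops out of both numerator and denominator. In the primary endpoint the same event counts as failure time.

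Two things are at stake. First, for these children the figure answers a narrower question than the objective asks. Second, readers will set the 6-month figure beside the whole-treatment figure and take the difference as durability of response. Part of that difference would come from the change of rule. SAP 8 says interim analyses will support regulatory filings, so the figures may be read this way before the study ends.

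**Working it through.** **1. The plan's own figure.** SAP 3.2 gives N = 200 and an SD of 30% to 36%. Half-width = 1.96 x SD / √200, which is 4.16 at SD 30 and 4.99 at SD 36. This reproduces the stated 4% to 5%. It refers to the 6-month percentage; no precision is stated for the 4.3 endpoints.

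**2. One child.** Inputs are the weekly 1 µg/kg steps from 1 to 10 µg/kg (Protocol 6.2.1 and Table 1) and the rule of four consecutive low weeks at maximum dose (Protocol 6.2.3).

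- Counts below 50 in weeks 2-4 take the dose from 1 to 4 µg/kg.
- Response in weeks 5-12 holds it there.
- Loss from week 13 brings six more increases, reaching 10 µg/kg in week 18.
- Low counts in weeks 19-22 trigger the stop. The last dose is in week 21 and EOT in week 22.

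Months are taken as four weeks, with month 1 = weeks 2-4, and 36 months as 156 weeks.

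| Rule | Calculation | Result |
|---|---|---|
| SAP 4.3, weeks 2-22 | 8/21 | 38.1% |
| SAP 4.2, months 2 and 3 of 6 | 2/6 | 33.3% |
| SAP 4.2 principle on weeks 2-24 | 8/23 | 34.8% |
| Same principle to Week 156 | 8/155 | 5.2% |

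The third row removes the effect of the monthly median. On that common weekly scale the excess over six months is 38.1 − 34.8 = 3.3 points.

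**3. Other patterns.** A child with no response week scores 0% under every rule. If EOT is in week 52 and response covers weeks 5-30, SAP 4.3 gives 26/51 = 51.0%, the primary 5/6 = 83.3%, and the 36-month version 26/155 = 16.8%. So the 4.3 value can exceed the 6-month value but need not. Against the same rule carried to Week 156 it is never lower, and it is higher whenever a child stopped before then had a response week.

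**4. Cohort size of this component.** Let f be the share of children stopped after losing response, T the last counted week, and p the percentage of counted weeks in response. The shift in the mean is f x p x (1 − (T − 1)/155). None of f, T or p is in the documents; the values below are assumptions.

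- f = 5%, T = 104, p = 60: 0.05 x 60 x (1 − 103/155) = 1.0 points
- f = 10%, T = 60, p = 60: 0.10 x 60 x (1 − 59/155) = 3.7 points
- f = 15%, T = 26, p = 52: 0.15 x 52 x (1 − 25/155) = 6.5 points

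The last line uses 52, not 60, because the stopping rule limits p. With the clock ended at the last dose, nine weeks below 50 and at least three low weeks at maximum dose leave at most 13 response weeks in weeks 2-26, and 13/25 = 52%. Counting the EOT week 27 as well gives 13/26 = 50% and 0.15 x 50 x (1 − 26/155) = 6.2.

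These are illustrations, not bounds. At T = 31, p = 60 becomes reachable (18/30), and f = 15% gives 0.15 x 60 x (1 − 30/155) = 7.3. If none of the stopped children ever responded, the shift is 0.

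**5. Net direction.** For a lack-of-response stop, both clocks end one week after the last dose. For a child in sustained response off drug they differ. Protocol 7.7 places EOT after month 36 for such a child who completes the period, so counting till EOT keeps the off-drug weeks. The SAP 6 definition ends at last dose plus one week and drops them, which works against the upward component.

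**The case against.** The strongest reply is that the on-treatment clock is the protocol's own. Protocol 10.1.1 ends both endpoints with the treatment period, and Protocol 3.1 describes response while receiving romiplostim. The 4.2 rule fills a fixed 6-month window, whereas 4.3 has a variable window and treatment lasts up to 36 months, so Week 156 as a common horizon is a choice. This stands: the 4.3 calculation should remain the protocol-defined main line. It does not reconcile that calculation with the objective in SAP 2.2.

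A second reply is that the consequence is limited. The study is descriptive with no hypothesis test, and withdrawal reasons, exposure and four-weekly response summaries will show early stopping. That is fair and limits the weight of the point. Those tables do not, however, put the long-term percentage on the same rule as the 6-month one.

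A reader might infer that the long-term cohort means are biased upward overall. The documents do not support that. The upward component is confined to children who respond and then fail, their number is not given, and the treatment of off-drug responders depends on which clock is used.

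**Conclusion.** The inconsistency is real. For children who respond, lose response and are stopped, SAP 4.3 overstates time in response over the study duration and can exceed the same child's 6-month value: 38.1% against 33.3% in the example, and 5.2% when scored to Week 156. The stronger readings, that 4.3 departs from the protocol's endpoint wording or that the long-term figure always exceeds the 6-month one, do not hold.

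The contribution to the cohort mean is roughly 1 to 6.5 points in the three scenarios. It rests on assumed stopping rates of 5-15%, assumed stopping times and assumed on-drug response. The planned half-width of 4 to 5 points for the 6-month figure gives a sense of scale only. The sign of the net bias stays open until the SAP settles the clock.

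**What to change.** In SAP 4.3, for both Week 2-to-EOT endpoints:

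1. Define the total number of weeks with one clock for all children, and reconcile it with the treatment-period definition in SAP 6.
2. Label the existing calculation as on-treatment and keep it as the main line.
3. Add a supplementary line over the planned 36 months (Week 2 to Week 156, or to study end if earlier). Score weeks after a stop for lack of response as no response, as in SAP 4.2, and count observed off-drug weeks of children in sustained response as observed.

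The cost is a few sentences and a little programming, with no new data. The downside is a second figure that is likely to be somewhat less favourable.

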6.2.1 Dosage, Administration, and Schedule

IP will be administered as a subcutaneous injection. The starting dose of romiplostim will be 1 µg/kg based on the subject's recorded screening weight. Initially, IP will be administered in the clinic by a qualified health care provider and subjects will return to the clinic weekly to provide blood samples for platelet counts and undergo any dose titrations under the supervision of the treating physician. Subjects who receive their first 8 doses in the clinic and achieve a stable dose of romiplostim for at least 4 weeks may be allowed to self-inject romiplostim or have the injection administered by a caregiver. Weekly dose increases will continue in increments of 1 µg/kg up to a maximum dose of 10 µg/kg in an attempt to reach a target platelet count of $\geq 50 \times 10^9/L$. Dose adjustments will be allowed to maintain a platelet count between $\geq 50 \times 10^9/L$ and $\leq 200 \times 10^9/L$. Dose adjustments will be evaluated every 12 weeks due to potential body weight changes.

Product: Romiplostim
Protocol Number: 20101221
Date: 15 August 2014

Page 26 of 69

If a dose of < 0.05 mL is required, dilution of romiplostim in a 1:2 ratio (a protein concentration of 0.25 mg/mL) or a 1:4 ratio (a protein concentration of 0.125 mg/mL) may be made with 0.9% saline to ensure an appropriate dispensable volume is delivered.

Subjects will be monitored for the onset of a sustained platelet response (see [Section 3.1.1](#)) and, if achieved, may dose-reduce romiplostim. If a subject no longer requires treatment with romiplostim but there is subsequently a fall in platelet counts of < 50 x 10⁹/L during the 36-month treatment period, treatment with romiplostim should resume at the initial weekly dose of 1 µg/kg.

The effects of overdose of romiplostim are not known. In high-dose preclinical studies, the noted effects were related to the pharmacological action of romiplostim. In the event of an overdose, platelet counts should be monitored frequently. Please refer to [Section 6.2.2](#) for dosage adjustments.

Specific romiplostim details, including labeling, storage, preparation, dilution, administration, etc., are provided in a separate Investigational Product Instruction Manual. Each romiplostim box number is to be recorded on each subject's Investigational Product Administration electronic case report form (eCRF).

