6.3 Self-administration of Romiplostim

Romiplostim will initially be administered by the investigator or qualified health care professional at clinic visits. At the investigator's discretion, subjects who have been dosed in the clinic and achieve a platelet count $\geq 50 \times 10^9/L$ without romiplostim dose adjustments for 4 consecutive weeks will be eligible to self-administer romiplostim or have the injection administered by a caregiver.

Those subjects who self-administer their medication, as well as those who are eligible to self-administer but choose not to, will only be required to return to the site for ongoing evaluations (including platelet counts) at designated study visits (performed every 4 weeks), as long as their dose of romiplostim remains stable.

In the event of a change in dose of romiplostim (per the dose adjustment rules in [Table 1](#)), subjects will be required to return to the clinic for 2 consecutive weeks to confirm that the dose adjustment was appropriate. Subjects will need to be on a stable dose and have a platelet count $\geq 50 \times 10^9/L$ for 2 consecutive weeks without romiplostim dose adjustments before resuming self-administration.

Before subjects begin romiplostim self-administration, it is the responsibility of the investigator to ensure that subjects or their caregivers are trained to prepare and administer the injection. Subjects and/or subject's caregivers will receive training and study tools designed to educate the subject on the proper storage, reconstitution, and self-administration of romiplostim. Once subjects or their caregivers have adequately demonstrated their ability to reliably administer the medication, subjects may be allowed to self-inject (or have the injection given by their caregiver) away from the investigational site. The completion of training on self- injection (or training to a caregiver) will be recorded in the subject's source documentation. All training will be monitored.

The site will be required to ensure that subjects are supplied with necessary materials required for self-injecting, including dispensing of the IP. All used vials of romiplostim must be returned to the clinic for drug accountability. Subject diary cards to record the dose, dosing date, and any dosing or storage errors will be provided to subjects.

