7.1 Schedule of Assessments

The Schedule of Assessments is found in [Table 2](#) below.

Table 2. Schedule of Assessments

Procedures	Screening	In Clinic Dosing Period ^a	Romiplostim Treatment Period (up to 36-months) ^b			End Of Treatment Visit	End of Study Visit
	- 4 Weeks	Week 1 to Week 8	Weekly	Every 4 Weeks	Every 12 Weeks		
Informed consent	X						
Confirmation of primary ITP diagnosis	X						
ITP/medical history	X						
Physical exam	X				X	X	
Vital signs	X				X	X	
Weight	X				X		
Central lab CBC with differential	X	X ^c		X ^b		X	
Central lab blood (serum) chemistry	X				X	X	
Local lab platelet counts	X	X	X ^{b,d}			X	X
Local lab peripheral blood smear		X ^c		X ^b		X	
Pregnancy test	X				X ^f	X ^f	
Concomitant /rescue medications	X	X	X	X	X	X	X
Adverse event reporting		X	X	X	X	X	
Serious adverse events	X	X	X	X	X	X	X
Antibody sample ^e		Day 1 (before first dose)			W12, W52 and every 24 weeks thereafter	X	
Romiplostim dosing		X	X				

ITP = immune thrombocytopenia; CBC = complete blood counts

- ^a Week 1 to Week 8. All subjects will return to the clinic for weekly dosing of romiplostim, platelet counts by a local laboratory, recording of concomitant/rescue medications, and adverse event reporting.
- ^b Subjects who complete 6 months of sustained platelet response (platelet count $\geq 50 \times 10^9/L$ in the absence of romiplostim or any ITP medications) will have assessments every 12 weeks for the duration of the 36-month treatment period.
- ^c Central CBC with differential and local lab peripheral blood smears are to be performed every 4 weeks, including pre-dose at week 1. Screening laboratory studies may be used in lieu of the pre-treatment day 1 week 1 laboratory tests if performed within 10 days prior to the first dose. Bone marrow biopsy suggested if abnormalities detected.
- ^d For subjects who establish a stable dose of romiplostim and are self-administering, have the injection administered by a caregiver, or meet this criterion but still prefer to come to the clinic for romiplostim administration, platelet counts will be monitored every 4 weeks.
- ^e For subjects who test positive for antibodies, see [Section 7.1.3](#). Antibody sampling during romiplostim treatment is only conducted if subject is receiving study drug.
- ^f Local lab urine or serum pregnancy test for female subjects of child-bearing potential (defined as having first menses)

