10.3.2 Analysis of Key Study Endpoints

10.3.2.1 Efficacy Endpoints

The primary endpoint for this study is the percentage of time with platelet response starting from week 2 in the first 6 months of the treatment period. Platelet response is defined as platelet count $\geq 50 \times 10^9/L$ at a scheduled protocol visit. Platelet counts within 4 weeks of a rescue ITP medication will not be deemed as platelet response. The 95% CI will be calculated for the estimated percentage of time.

Summary statistics of platelet counts and responses will be provided at weeks 1 to 8 and then every 4 weeks.

The percentage of time with platelet response starting from week 2 until the EOT period will be summarized with 95% CI.

Product: Romiplostim
Protocol Number: 20101221
Date: 15 August 2014

Page 48 of 69

Missing platelet counts at weeks 12 and 16, and every 4 weeks thereafter will be imputed by using the mean of the 2 closest non-missing platelet counts within ± 1 week before study discontinuation. If still missing after imputation, platelet counts will be considered as non-response.

The proportion of subjects with splenectomy during the study will be summarized for the subjects who entered this study without splenectomy.

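### Carrying the last platelet count forward overstates time in response in both Week 2-to-EOT endpoints, because stable responders are counted every 4 weeks and most other children weekly

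*SAP*

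**What the plan says.** **Scoring.** For the platelet-response endpoint, SAP 4.3 defines each child's percentage as "the number of weeks with a platelet response divided by the total number of weeks". The ≥20 x 10⁹/L increase endpoint has the same form. Under both, the SAP adds: "Weekly platelet counts are imputed by last observation carry forward using rescue-evaluable weekly platelet counts during the treatment period".

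**Count frequency.** Protocol 6.2.1 starts everyone on weekly counts: "subjects will return to the clinic weekly to provide blood samples for platelet counts". Protocol 6.3 then relaxes this for some. Children dosed in clinic who hold a count of at least 50 x 10⁹/L "without romiplostim dose adjustments for 4 consecutive weeks will be eligible to self-administer romiplostim", and those who qualify, whether or not they self-inject, "will only be required to return to the site for ongoing evaluations (including platelet counts) at designated study visits (performed every 4 weeks". Table 2 footnote d applies the same interval to children who qualify "but still prefer to come to the clinic for romiplostim administration, platelet counts will be monitored every 4 weeks".

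**Return to weekly counts.** Under Table 1 a count below 50 calls for a dose increase. After any dose change, Protocol 6.3 says "subjects will be required to return to the clinic for 2 consecutive weeks", and two weeks at 50 or above on a stable dose are needed before self-administration resumes.

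**The protocol's own rule.** Protocol 10.3.2.1 does not mention carry-forward. "Missing platelet counts at weeks 12 and 16, and every 4 weeks thereafter" are replaced by the mean of the two closest counts within one week either side, and are otherwise scored as non-response. Counts within 4 weeks of rescue are not responses. SAP section 11 nevertheless declares no change from the protocol.

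**The concern.** The interval between counts depends on the outcome being measured. In a stable responder, up to 3 of every 4 weeks are carried-forward responses by design. Weeks out of response, once seen, are mostly observed directly. Carry-forward thus delays the recorded loss of response without a matching delay in the recorded recovery, and the two errors do not cancel.

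These gaps are not missed visits, so good adherence does not remove the bias and a larger sample does not shrink it. The study is descriptive: the estimated percentage is itself the result, and the rule shifts it directly. The plan names no alternative scoring for these two endpoints; the per-protocol sensitivity analysis concerns only the primary endpoint.

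**Working it through.** **1. The plan's own figure.** The plan gives no figure for these two endpoints. For the first-6-month percentage, SAP 3.2 states an SD of 30% to 36%, n = 200 and a 95% CI half-width of 4% to 5%. Half-width = 1.96 × SD / √n:
- 1.96 × 30 / √200 = 4.16
- 1.96 × 36 / √200 = 4.99

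This reproduces, and it shows that the 30% to 36% is a between-subject SD. Step 4 uses it as a plausibility check.

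**2. One episode by hand.** A child on 4-weekly counts is at or above 50 at week 20, falls below at week 21, is seen at week 24, and recovers at week 26 while on weekly counts.
- True weeks out of response: 21 to 25, which is 5.
- Weeks out recorded under carry-forward: 24 and 25, which is 2.
- Weeks wrongly credited: 3. Over weeks 2 to 156 (155 weeks) that is 3/155 = 1.9 points.

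A loss in weeks 21, 22, 23 or 24 is dated 3, 2, 1 or 0 weeks late, a mean of 1.5 weeks. Recovery is dated 0 weeks late.

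**3. Approximate size.** Bias ≈ weekly loss risk × share of time in response × 1.5 weeks. With a 74% share (SAP 3.2's planning mean, borrowed from the first 6 months):
- loss risk 1%: 0.01 × 0.74 × 1.5 = 1.1 points
- loss risk 2%: 0.02 × 0.74 × 1.5 = 2.2 points

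A two-state weekly simulation (1,500 children, 156 weeks, the protocol's visit switching) gave +1.0 and +2.0. The hand formula runs slightly high because some response weeks are still counted weekly.

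**4. Which switching rates fit the plan?** The documents give none, so these are assumptions. In a second two-state simulation (3,000 children, all starting out of response, long-run share 74%), the bias was set beside the between-subject SD over weeks 2 to 26:

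| Assumed model | Carry-forward minus truth | SD |
|---|---|---|
| Mean response spell 52 weeks | +1.8 | about 34 |
| Mean response spell 26 weeks | +3.6 | about 29 |
| Children differ (beta-distributed share, mean non-response spell 3 to 9 weeks) | about +2.4 to +4.4 | near 30 |

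Mean spells of 16 and 8 weeks give larger biases, but their SDs are about 23 and 15, well under 30% to 36%, so they are set aside. A mean spell of 100 weeks gives +0.9, and the SD check does not exclude a case that stable.

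**5. The ≥20 increase endpoint.** Visit frequency is tied to 50, so counts between baseline + 20 and 50 are still taken weekly. An autocorrelated count model (variability assumed) scored both endpoints on the same simulated children. With log-scale SD 0.4, the bias was +3.3 (≥50) against +0.8 (≥20 increase) at autocorrelation 0.8, and +2.6 against +0.4 at 0.9. Over all settings tried, the second endpoint's bias was +0.2 to +3.2, and less than half of the first's in each matched run.

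**6. The same data on a common grid.** Scored weekly to week 8 and then every 4 weeks for every child, the result was within 0.5 points of truth throughout. On a fixed grid, losses and recoveries are delayed alike.

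**The case against.** The case against is mainly about size and scope, and several parts of it stand.

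- **Who is counted when.** A reader might sum this up as responders every 4 weeks and non-responders weekly. That is too broad. A responder whose dose changes, including a reduction after two weeks above 200, returns to weekly visits. Under Protocol 6.2.3 a non-responder kept on study at a stable dose may become eligible for self-administration. The simulations model neither. They alter the size, not the direction.
- **Large biases.** One might infer a bias well above 5 points by assuming frequent switching. Those scenarios imply far less variation between children than SAP 3.2 states.
- **Long carry-forward off drug.** One might infer carry-forward of up to 11 weeks during the 12-weekly follow-up. SAP section 6 ends the treatment period one week after the last dose, so drug-free follow-up is outside it unless romiplostim is resumed.
- **Comparison with the planned precision.** The 4% to 5% half-width belongs to the primary endpoint, which uses monthly medians and is untouched by this rule. It is not a benchmark for these endpoints.
- **No decision at stake.** Both endpoints are secondary and descriptive, with no test or threshold. This limits the urgency.
- **Already reported on a grid.** Protocol 10.3.2.1 and SAP 10.5 summarise counts and responses at weeks 1 to 8 and every 4 weeks. A careful reader could compare, but those visit-level summaries do not correct the per-subject percentage of time, which is the endpoint.

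**Conclusion.** The concern holds in direction for both endpoints: following the plan exactly overstates the percentage of time in response. For the ≥50 endpoint the plausible size is roughly 2 to 4.5 points in scenarios with a between-subject SD near 30% to 36%, and under 1 point if responses are very stable. For the ≥20 increase endpoint it is smaller.

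The direction follows from the visit rules and was upward in every scenario run. The size is not fixed by the documents. It rests on assumed switching rates, on a long-run share near 74% taken from the first-6-month planning figure, and on 4-weekly visits falling on study weeks counted from day 1, as Protocol section 7 sets out.

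Separately from size, SAP 4.3 departs from the missing-count rule in Protocol 10.3.2.1 while SAP section 11 reports no change.

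**What to change.** In SAP 4.3, for both Week 2-to-EOT endpoints:

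1. Make the main analysis use the grid in Protocol 10.3.2.1: weekly for weeks 2 to 8, then every 4 weeks, with each 4-weekly count standing for its interval.
2. Apply the Protocol 10.3.2.1 rules on that grid. A missing count takes the mean of the two closest counts within one week either side, otherwise non-response; a count within 4 weeks of rescue is non-response. The protocol's imputation rule names only week 12 onward, so say how a missing count in weeks 2 to 8 is scored.
3. Keep carry-forward as a sensitivity analysis.
4. Reconcile SAP section 11 by listing any remaining departure from Protocol 10.3.2.1.

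The cost is SAP wording and programming; no new data are needed. The downsides are that weekly counts off the grid after week 8 drop out of the main analysis, and the reported percentage may be a few points lower.
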